4.3 Trial population

The trial population will be adults 18 years and older who have been boosted at least six months earlier with a third COVID-19 vaccine dose. There will be no upper age limit for groups A and B. Only those aged \geq 18 - 60 years will be recruited to group C (controls), as this is the target age group for which the need for additional boosters is not well established. Additional booster doses are strongly recommended for individuals 60 years and over. Procedures will be implemented to ensure an even age distribution for Moderna product transition in each vaccine group.

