6 RANDOMISATION AND BLINDING

The two vaccine groups will be randomised 1:1 to one of two interventions (bivalent Omicron-specific Moderna and Novavax) stratified by age (<50 and \geq 50 years). An independent statistician from the Melbourne Children's Trial Centre at the Murdoch Children's Research Institute will provide a secure, password-protected web-based randomisation schedule. Blocked randomisation will be used with random blocks of permuted length.

50% of participants from each vaccine group will be included in the cell-mediated immunity (CMI) subgroup analysis. We will ensure that the age strata (<50 and \geq 50 years) are equally represented in the CMI vaccine groups. As only 10-20 CMI samples can be processed per day, we will recruit the first 10-20 participants per day to participate in this substudy.

The control group will not be randomised and will be recruited from participants <60 years of age who indicate that they are not planning to receive a fourth vaccine dose at the time of recruitment. Controls will be recruited into proportional predefined age bands (18-29 years, 30-49 years, 50-59 years).

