11 STATISTICAL METHODS

11.1 Sample Size Estimation

Sample size calculations were performed using nQuery 8 software and methods described by Van Belle, et al. 1993 (20). Precision-based sample size calculations were performed based on the reactogenicity outcomes. Assuming the percentage of participants reporting local or systemic reactions is 50%, 100 participants will produce a confidence interval that is 9.8 percentage points from the observed percentage. For immunogenicity, sample size calculations were based on comparing day 28 post-booster geometric mean concentrations of IgG antibodies between vaccine arms. We assumed the coefficient of variation (standard deviation/mean) of the post-booster antibody concentrations would be 1.15 (based on data from Munro, et al. 2021 (8), but increased to be conservative). Even though previous studies demonstrated a geometric mean ratio (GMR) of up to 4 between the study vaccine groups, we considered a clinically important difference between groups to be a GMR of >1.4. Based on these assumptions the study will need to recruit 160 participants in each vaccine group overall to achieve 90% of power at two-sided 0.05 significance level. Allowing for ~20% loss to follow-up the sample size in each arm was expanded to 200. To ensure age representation (<50 and ≥50) in the second Moderna bivalent group (BA.4-5) numbers were increased in the younger age group.

We are confident that the sample size is sufficient as it is likely that the GMR difference will be higher than expected and the loss to follow-up lower than anticipated.

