11.3 Methods of analysis - outcome variables and methods

11.3.1 Primary outcome

Reactogenicity following immunisations will be presented as the number and percentage of participants self-reporting local reactions (pain, tenderness, redness, hardness, swelling, warmth, itch at or near the injection site) and systemic reactions (fever, nausea, vomiting, diarrhoea, headache, fatigue/malaise, myalgia), and the severity of these reactions (mild, moderate, severe, life-threatening, or fatal). Reactogenicity data will be presented separately by group and time point. For reactogenicity proportions will be estimated with 95% Clopper-Pearson binomial confidence intervals.

For immunogenicity, antibody levels will be presented as geometric mean concentrations (GMC) with 95% confidence intervals. Changes from baseline will be expressed as geometric mean fold ratios (GMFR), calculated as the ratio of the post-booster GMC to the baseline GMC. GMCs will be compared between the two vaccine groups at 28 days. We will account for baseline levels, age, primary series and first booster vaccine in the analysis. We will use the Treatment Policy strategy for the analysis, meaning that each intercurrent event (i.e., breakthrough SARS-CoV-2 infection) is considered to be part of the treatment effect.

The binding IgG data using the Euroimmun S1 IgG ELISA kits will be reported as relative units/ml (RU/ml) per the manufacturer's instructions. A result of <8 RU/ml: negative (IgG Antibodies for SARS-CoV-2 are not detected), ≥8 to <11 RU/ml: borderline (IgG antibodies are indeterminate/equivocal with this sample, ≥11 RU/ml: positive (IgG antibodies for SARS-CoV-2 are detected). Conversion to binding antibody units (BAU/ml) will also be done using the WHO reference serum from NIBSC, UK. Data will be presented as geometric mean concentrations and 95% confidence intervals. The primary endpoint will be the GMR at Day 28 for binding antibody. Linear regression will be used to estimate the differences in log antibody concentrations, adjusted for stratifying variables (age group), duration between different doses, study day of blood-draw, and baseline levels. The GMR will be calculated as the antilogarithms of the mean difference (beta1) and its 95% CI.

In addition to the group level assessments described above, for individual patients in the vaccine groups, seroresponse will be defined as:

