Population-level summary measure Geometric mean ratio	Analysis approach Linear regression will be used to estimate the GMR comparing the two vaccine groups, adjusted for the stratifying variable (age group), baseline levels, first booster vaccine and time since first booster. The outcome variable (and the baseline value) will be \log_e transformed before regression, and the GMR (95% CI) will be calculated as the antilogarithms of the mean difference (β_1) and its 95% CI.

[#]Supplementary analyses will be conducted using the Hypothetical Strategy for handling intercurrent events (see Table 14).

Table 7. Estimand-to-Analysis⁵ table for at least one solicited grade 3 or 4 local or systemic reaction within 7 days of boosting (primary reactogenicity endpoint)

Primary Objective (as per Protocol): Assess the rate and severity of reactogenicity within one-week post-second booster for the Moderna and Novavax groups (Timepoint – daily, for seven days post-vaccination).	
Estimand:	Incidence risk of a grade 3 or 4 local or systemic reaction within 7 days (inclusive) of boosting, by vaccine group in adults 18 years or older who have received their third dose of COVID-19 vaccine at least six months previously
ESTIMAND Attributes:	Incorporation of Estimand Attribute in ANALYSIS:
Treatment Bivalent mRNA Moderna COVID-19 vaccine and protein-based Novavax COVID-19 vaccine	Study arms Bivalent Moderna vaccine arm (Moderna BA.1 and Moderna BA.4-5 groups combined) Novavax vaccine arm
Target population Adults 18 years or older who have received their third dose of COVID-19 vaccine at least six months previously	Analysis set (“Reactogenicity Population”) All participants, as per trial vaccine received (regardless of allocation).
Variable Grade 3 or 4 local or systemic reaction within 7 days (inclusive) of boosting.	Outcome measure Presence of at least one solicited grade 3 or 4 local or systemic reaction within 7 days (inclusive) of boosting.
Handling of intercurrent events	
Event (up to and including Day-7)	Strategy⁴
SARS-CoV-2 infection	While Negative (values up to the day of the first positive test are used)
Death	While Alive (values up to the time of death are used)

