Handling of intercurrent events	Handling of missing data The proportion of participants excluded due to missing outcome or covariate data will be described by study group. If >5% of participants are excluded due to missing data, a supplementary analysis will be performed with multiple imputation.
Population-level summary measure Geometric mean ratio (GMR) OR Difference in Means*	Analysis approach Linear regression will be used to estimate the difference in mean [OUTCOME]* between the vaccine arms, adjusted for the stratifying variable (age group), primary series and first booster vaccine, and baseline [OUTCOME]* levels. Where the population-level summary measure is the GMR, the outcome variable (and the baseline value) will be log_e transformed before regression, and the GMR (95% CI) will be calculated as the antilogarithms of the mean difference (β_1) and its 95% CI. When zero and negative values are expected, the population-level summary measure will be the difference in medians. This will be estimated using quantile regression with the same adjustment variables as above. The distribution of the immunological data at each timepoint will be displayed using a scatterplot

	overlaid with median and interquartile range (see Dummy Figure 3)
--	---

*This table is generic for all secondary Month-6 and Month-12 immunological endpoints (see Table 8), which will be analysed in the same way depending on their distributions; the population measure for outcomes with skewed distributions is the geometric mean and the population-level summary measure of association (MoA) is the GMR – baseline and Month-[6/12] values will be log_e transformed before analysis; the population measure for normally distributed outcomes is the mean and the population-level summary measure of association (MoA) is the Difference in Means. For outcomes with skewed distributions and negative values, the population summary measure of association is the difference in medians, which will be estimated using quantile regression.

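### The SAP's written immunogenicity models use age only as <50/≥50, a small precision loss for Moderna vs Novavax; the vaccine-vs-control comparisons have no stated age term and should use age in years

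*Protocol*

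**What the plan says.** **Age range.** Protocol 4.3 says of the vaccine arms: "There will be no upper age limit for groups A and B". Controls must be under 60. They are not randomised, and Protocol section 6 says of them: "Controls will be recruited into proportional predefined age bands (18-29 years, 30-49 years, 50-59 years". The vaccine arms are randomised 1:1, stratified only at 50 years.

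**Age in the written models.** The primary Day-28 model (SAP 7.2, Table 6) is "adjusted for the stratifying variable (age group), baseline levels, first booster vaccine and time since first booster". Table 9, for the other Day-28 endpoints, uses the same age term. Table 10, for Month 6 onwards, is "adjusted for the stratifying variable (age group), primary series and first booster vaccine, and baseline" level of the outcome. The quantile regressions in Tables 9 and 10 take the same covariates. The imputation model (SAP 4.10) includes age group, and age in years is not among its listed auxiliary variables.

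**Age in the protocol.** Protocol 11.3.1 uses two wordings. One sentence reads "We will account for baseline levels, age, primary series and first booster vaccine in the analysis"; a later one in the same section adjusts for age group as the stratifying variable. SAP 1.3 notes that the protocol gave two adjustment sets and settles on age group for the primary model.

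**Control comparisons.** SAP Table 8 lists Group A vs control and Group B vs control from Month 6 onwards. Tables 6, 9 and 10 name only the Moderna and Novavax arms, and their analysis sets are randomised participants. For the control contrasts the only covariate statement is in Protocol 11.3.2: age will be taken into account, with no form given.

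**Data held.** Age is recorded at Day 0 (SAP 6.4), Dummy Table 1 reports it in years, and dates of birth are collected (Protocol 9.1.1).

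**The concern.** A single cut at 50 treats an 18-year-old like a 49-year-old, and a 50-year-old like someone over 80. If antibody level changes with age inside those strata, two things follow.

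- In the randomised comparison, that variation stays in the residual and widens the interval.
- In a non-randomised comparison, a difference in mean age inside a stratum goes straight into the estimate and would be read as a fourth-dose effect.

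The second matters more. The control contrasts carry the question of whether a fourth dose adds anything, and the documents give reasons why age mix could differ inside the under-50 stratum. Controls are filled by bands within it and vaccinees are not. Protocol 2.3.3 says second boosters were available outside the trial from age 30, and at 16–29 only with certain medical conditions. Controls are people not planning a fourth dose. The incentive to join either group may therefore change at 30. The direction is unknown.

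**Working it through.** **1. The plan's own figure.** Inputs from Protocol 11.1: "the study will need to recruit 160 participants in each vaccine group overall to achieve 90% of power at two-sided 0.05 significance level"; coefficient of variation of "the post-booster antibody concentrations would be 1.15"; and "we considered a clinically important difference between groups to be a GMR of >1.4".

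- Log SD = √ln(1 + 1.15²) = √0.843 = 0.918; ln 1.4 = 0.3365.
- n = 2(1.960 + 1.282)² × 0.843 / 0.3365² ≈ 157 per arm (158 with the t distribution). The stated 160 is reproduced, and 160/0.8 = 200.
- Power is 90.6% at 160 per arm, 93.5% at 180 (225 less 20%) and 97.3% at 225.

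**2. Precision lost in Moderna vs Novavax.** The documents give neither the age distribution nor the slope of titre on age. Assumptions: ages uniform within strata, 80 as the practical upper age, and titres 5, 10 or 15% lower per decade.

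- Within-stratum SD of age: (49 − 18)/√12 = 8.9 years; (80 − 50)/√12 = 8.7 years.
- Slope per year: b = −ln(1 − d)/10 = 0.0051, 0.0105, 0.0163.
- Share of log variance: R² = (b × 8.9)²/0.843 ≈ 0.0025, 0.0105, 0.025.
- Interval width with age in years, relative to without: √(1 − R²) = 0.999, 0.995, 0.987. The current model's interval is about 0.1, 0.5 or 1.3% wider on the log scale.

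A second route gives the same picture. Let ρ be the partial correlation of age with log IgG, and k the share of age variance captured by the 50-year cut. With a 2:1 mix of <50 and ≥50 and several assumed age ranges, k = 0.69–0.73. Replacing the cut by linear age multiplies the residual variance by (1 − ρ²)/(1 − kρ²).

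| ρ | Variance factor | 160 per arm becomes | Power gain at 180 per arm |
|---|---|---|---|
| 0.1 | 0.997 | about 159.5 | 0.06–0.07 points |
| 0.2 | 0.987–0.989 | about 158 | 0.2–0.3 points |
| 0.3 | 0.970–0.974 | 155–156 | 0.5–0.6 points |

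Both routes use the unadjusted log SD. Adjustment for baseline titre would shrink the residual, which raises these shares. It may also absorb part of any age effect, which lowers them. The documents settle neither.

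**3. Control contrasts, if the age-group term is carried over.** The multiplicative bias in the geometric mean ratio is exp(b × gap). For an assumed 5-year gap in mean age within a stratum:

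| Assumed fall per decade | exp(5b) | Reverse direction |
|---|---|---|
| 3% | 1.015 | 0.985 |
| 5% | 1.026 | 0.975 |
| 10% | 1.054 | 0.949 |
| 15% | 1.085 | 0.922 |

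The shift is about 1.5–8%. The ratio is pushed down if controls are the younger group and up if they are the older.

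**4. The ≥50 stratum.** Controls stop below 60 and vaccinees do not. With assumed means of about 55 and 65 the gap is about 10 years, and slopes of 3–10% per decade give factors of 0.97–0.90. Age in years alone would only extrapolate here, because no controls are aged 60 or over. Restriction to under 60 is needed as well.

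**The case against.** The strongest reply is that the written models are sound for what they cover. Moderna vs Novavax is randomised and stratified at 50, and adjusting for the stratification factor is standard. A reader might infer that cutting age at 50 biases this comparison. It does not, and the precision cost is small in a trial planned at 90% power. An interval gain of 2–3% would need a within-stratum correlation of 0.20–0.25, which at these SDs means titres about 19–23% lower per decade, beyond the slopes assumed above. All of this stands.

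A reader might also infer that the SAP confounds the control comparisons through its binary age term. The documents do not support that, because no covariate set is written for those comparisons. The firm finding is the missing specification; residual confounding is conditional on Table 10, the only long-term template, being reused. Nor do the documents show an age imbalance. The bands 18–29 and 30–49 may reduce it, although what they are proportional to is not stated. Even as assumed, the shift is small beside the trial's threshold ratio of 1.4.

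Finally, one might say that the SAP narrowed the protocol's age adjustment. For the primary model that is unfair: Protocol 11.3.1 already contains the age-group wording, and SAP 1.3 declares the choice.

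What survives is that the control model has still to be written, that a two-level term would be the wrong default in a non-randomised comparison, and that the better variable is already in the database.

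**Conclusion.** The point holds as a minor improvement. Every immunogenicity model written out in the SAP, and the imputation model, reduces age to <50/≥50 although age in years is available.

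- **Moderna vs Novavax:** valid and unbiased as planned. The cost is an interval about 0.1–1.3% wider, given uniform ages within strata and a fall of 5–15% per decade.
- **Vaccine vs control:** no age term is specified. If the two-level term is reused, a 5-year gap within a stratum would shift the ratio by about 1.5–8%, given a fall of 3–15% per decade. Both the gap and the slope are assumptions, and neither can be checked from the documents.

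No stated figure in the sample-size section is affected.

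**What to change.** 1. **Control comparisons from Month 6.** Write the model for A vs control and B vs control. Use the age-group term plus age in years (linear, or a restricted cubic spline with 3 knots), among participants under 60 so that ages overlap.
2. **Imputation and quantile models.** Use the same age term in SAP 4.10, which the hypothetical-strategy analyses reuse (SAP 9.4.1), and in the quantile regressions.
3. **Tables 6, 9 and 10.** Add age in years alongside the stratum term as a minor precision gain. SAP version 1.0 covered data up to Day 28; if those results have already been analysed under it, report this at Day 28 as a sensitivity analysis and leave the primary model unchanged.

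The cost is SAP wording and one to two degrees of freedom, out of about 450 vaccinees for the full-cohort endpoints. It is slightly more noticeable in the subsets: about 225 vaccinees (50% of 450) for cellular immunity, and about 90 (20% of 450, if the 20% of samples corresponds to 20% of participants) for neutralisation. A linear term is the safer choice there. Restricting the control contrasts to under 60 sets aside older vaccinees, who have no control counterparts.

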4.4 Eligibility criteria

If informed consent is granted, study staff will ensure all the eligibility criteria are met. Potential participants must meet all the inclusion criteria and none of the exclusion criteria to be eligible.

4.4.1 Inclusion criteria

Each participant must meet all the following criteria to be enrolled in this trial:

1. Have received a third COVID-19 vaccine dose at least six months before the start of the study.

2. No confirmed SARS-CoV-2 infection by PCR or RAT within the last three months.
3. Willing and able to give written informed consent.
4. Aged 18 years or above.
5. Willing to complete the follow-up requirements of the study.

Note that subjects with comorbidities other than those listed below as contraindications will be included. Pregnant women or women who may become pregnant will be included.

4.4.2 Exclusion criteria

Potential participant meeting any of the criteria below will be excluded from this trial:

1. Currently receiving immunosuppressive medication or anti-cancer chemotherapy.
2. Known HIV infection.
3. Congenital immune deficiency syndrome.
4. Received immunoglobulin or other blood products in the three months prior to potential study booster vaccination.
5. Study staff and their relatives.
6. Have a history of a severe allergic reaction to any COVID-19 vaccines or have a medical exemption to receiving further COVID-19 vaccines.
7. Cannot read or understand English.

4.5 Lifestyle considerations

Not Applicable.

4.6 Screen failures

Screen failures are defined as participants who consent to participate in the trial but are found during screening procedures to be ineligible. They, therefore, do not receive the intervention and are not randomised. We anticipate that there will be very few screen failures due to the nature of the inclusion/exclusion criteria.

4.7 Recruitment and identification of potential participants

Prior to starting the study a comprehensive recruitment plan will be developed. The study will be advertised across the Melbourne Children's Campus (MCRI, Royal Children's Hospital, University of Melbourne), Royal Melbourne Hospital, the Doherty Research Institute, the Parkville precinct and, the broader Melbourne community. We will initially target people working in the medical, science, and healthcare fields and expand recruitment to the general public as needed. We will target specific study or age groups as needed as the study proceeds. Study information (via email, healthcare facilities notice board and/or website/social media, patient/participant registries and recruitment services etc.) will include an information sheet about the study and a link to the study website where they can evaluate their eligibility and obtain additional study details, such as the participant information sheet and consent form (PICF). The potential participant can register their interest and will be given the opportunity to talk with a research team member by phone or zoom if they have any further questions.

All potential participants will be recorded on a recruitment/enrolment log. No identifying information will be retained if the potential participant decides not to participate.

In addition, participants will also be recruited directly from interested general practices. Potentially eligible participants will be sent an email or SMS with the study details from their GP practice and be given the option to contact the COVID-19 booster study team if they want more information or wish to join the study. The COVID-19 booster study team will not have access to GP patient records. In select cases satellite clinics may be conducted at GP clinics with facilities to conduct vaccinations. Similarly at community clinics with access to medical facilities.

Participants from other relevant MCRI studies (for example the BRACE trial), who consented to be contacted for future research, will be contacted by the original study teams. The original study team will send the participants an email with the study details and give them the option to contact the COVID-19 booster study team if they want more information or wish to join the study. The COVID-19 booster study team will not have access to the participant details.

4.8 Consent

Informed consent is a process initiated prior to the agreement to participate in the trial and continues throughout study participation. Before obtaining informed consent, the vaccination's possible risks and benefits will be discussed with potential participants. Trial staff will go through the Informed Consent Form (ICF), which describes in plain language the trial interventions, the study procedures, and the risks and benefits of participation. The ICF will be HREC-approved, and the potential participant will be asked to read and review the ICF. The trial staff will explain the research study further and answer any questions.

Written documentation of informed consent is required prior to enrolment into the trial. The potential participant will sign and date the final page of the ICF. The trial staff will witness the consent, confirming that the trial has been fully explained and that the participant understands the rationale and processes for the trial. The potential participant will be informed that they are free to withdraw from the trial at any time. A copy of the ICF will be given to the potential participant.

